4.1. Introduction

Data processing and tabulation of descriptive statistics described in this SAP will primarily use SAS (release 9.4 or higher). If the use of other software is warranted, the final statistical methodology report will detail what software was used for what purposes.

Continuous (quantitative) variable summaries will include the number of subjects (n) with non-missing values, mean, standard deviation (SD), median, minimum, and maximum.

Categorical (qualitative) variable summaries will include the frequency and percentage of subjects who are in the particular category or each possible value. Summaries may include 95% confidence intervals (CIs) if appropriate. In general, the denominator for the percentage calculation will be based upon the total number of subjects in the study population, either overall or within each absorbency arm, unless otherwise specified.

The minimum and maximum will be reported with the same degree of precision (i.e., the same number of decimal places) as the observed data. Measures of location (mean and median) will be reported to 1 degree of precision more than the observed data. Measures of spread (SD, 95% CI) will be reported to 2 degrees of precision more than the observed data.

Percentages will be presented to 1 decimal place, unless otherwise specified. General exceptions to this rule are values of 100% which will be displayed without any decimal places and zero counts which will not display percentages.

No inferential statistical hypothesis testing will be performed to assess whether the validation criteria have been met. All the analyses described in this SAP to assess whether validation criteria have been met are descriptive.

4.2. Interim Analysis and Data Monitoring

No interim analyses are planned.

5. Analysis Populations

The following analysis populations are planned for this study:

- **Intent-To-Treat Population (ITT):** The ITT population includes all subjects randomized into the study.
- **Safety Population:** The Safety Population includes all ITT subjects who insert at least 1 tampon.
- **Modified Intent-To-Treat Population (MITT):** The MITT population includes all safety subjects who have no major protocol deviations and return at least 1 tampon that can be assessed for elongation.

Assignment of subjects to populations will be determined at a data review meeting prior to database lock.

6. General Issues for Statistical Analysis

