### Analysis Populations

Intent-to-Treat (ITT): Subjects randomized into the study.

Safety: ITT subjects who insert at least 1 tampon

Modified Intent-to-Treat (MITT): Safety subject who returns at least 1 tampon that can be assessed for elongation.

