### Primary Endpoint

The proportion of used tampons that have elongated will be used to assess the following user need:

- User can remove product from the vagina after use

Analysis will be done separately for each absorbency for the MITT population.

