8.1. Elongation

Descriptive statistics will be reported for the length of elongation of used tampons within each test article type (test or reference tampon), and separately for each absorbency arm, in the MITT population. The number and percentage of used tampons that have elongated will be reported for test tampons and reference tampons. Determination of whether a tampon is considered to have elongated is described in Section 6.1.4. The denominator for the percentage calculation will be based upon the number of used tampons returned within each test article type (test or reference tampon) and within each absorbency arm (regular or super). The 95% CIs for the percentage elongated estimates will be computed using the exact method (Clopper & Pearson, 1934).

In addition, the testing of equality of proportions of elongation between test and reference article types within each absorbency arm will be performed. For this purpose, the difference between proportions will be calculated along with 95% Wald CIs. Pearson chi-square test will be computed in support of hypothesis testing. The samples for comparison will be considered independent.

The following hypothesis will be tested:

H0: $p1-p2=0$. There is no significant difference in the tampon's elongation rate between the test and reference article types within each absorbency arm.

H1: $p1-p2\neq0$. There is a significant difference in the tampon's elongation rate between the test and reference article types within each absorbency arm.

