9.7. Product Complaints

Information on product complaints that were not captured in the subject diaries or as adverse events will be provided in a separate listing.

10. Changes from Planned Analysis

Not applicable.

11. Other Planned Analysis

Not applicable.

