13.2. Validation Criteria Data

Table 3: Validation Criteria Data

Table Number	Population	Table Title / Summary
Table 14.2.1	MITT	Summary of Elongated Tampons
Table 14.2.2.1	Safety	Summary of Individual Tampon Entry Diary Responses
Table 14.2.2.2	Safety	Summary of Diary Responses Following Last Tampon Use
Table 14.2.3	ITT, Gynecological Exam Subset	Summary of Packaging and Labeling Interview Responses

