14.2. Planned Table Shells

See [Figure 2](#) below.

[figure not shown]

Figure 2: Planned Table Shells

Table 14.1.1
 Subject Disposition
 All Subjects

Status Category	Regular Absorbency (N=XX)	Super Absorbency (N=XX)	Overall (N=XX)
Screened for Eligibility			xx
Screen Failure			xx
Enrolled	xx	xx	xx
Randomized	xx	xx	xx
ITT Population [1]	xx (xx.x%)	xx (xx.x%)	xx (xx.x%)
Gynecological Exam Subset [2]	xx (xx.x%)	xx (xx.x%)	xx (xx.x%)
Safety Population [3]	xx (xx.x%)	xx (xx.x%)	xx (xx.x%)
Gynecological Exam Subset [2]	xx (xx.x%)	xx (xx.x%)	xx (xx.x%)
MITT Population [4]	xx (xx.x%)	xx (xx.x%)	xx (xx.x%)
Completed Study	xx (xx.x%)	xx (xx.x%)	xx (xx.x%)
Discontinued Early	xx (xx.x%)	xx (xx.x%)	xx (xx.x%)
Adverse Event	xx (xx.x%)	xx (xx.x%)	xx (xx.x%)
Withdrew Consent	xx (xx.x%)	xx (xx.x%)	xx (xx.x%)
Protocol Violation / Non-Compliance	xx (xx.x%)	xx (xx.x%)	xx (xx.x%)
Investigator / Sponsor Decision	xx (xx.x%)	xx (xx.x%)	xx (xx.x%)
Lost to Follow-Up	xx (xx.x%)	xx (xx.x%)	xx (xx.x%)
Other	xx (xx.x%)	xx (xx.x%)	xx (xx.x%)

Abbreviations: ITT = intent-to-treat; MITT = modified intent-to-treat.

Note: Percentages are n/Number of subjects in the ITT Population within absorbency arm and overall subjects *100. .

[1] The ITT Population includes all subjects randomized into the study.

[2] A subset of subjects was selected to undergo gynecological exams prior to and following tampon use. In addition, only the subjects in this subset completed the packaging and labeling interview.

[3] The Safety Population includes all ITT subjects who insert at least 1 tampon.

[4] The MITT Population includes all subjects in the Safety population who have no major protocol deviations and return at least 1 tampon that can be assessed for elongation.

n is the number of subjects within each category. N is the number of subjects within absorbency arm.

Reference Listing: 16.2.1.1

Table 14.1.2
 Demographics and Baseline Characteristics
 ITT Population

Variable Statistic or Category	Regular Absorbency (N=XX)	Super Absorbency (N=XX)	Overall (N=XX)
Age (years) [1]			
n	XX	XX	XX
Mean (SD)	XX.X (XX.XX)	XX.X (XX.XX)	XX.X (XX.XX)
Median	XX.X	XX.X	XX.X
Min, Max	XX, XX	XX, XX	XX, XX
Gender			
Female	XX (XX.X%)	XX (XX.X%)	XX (XX.X%)
Undifferentiated	XX (XX.X%)	XX (XX.X%)	XX (XX.X%)
Unknown	XX (XX.X%)	XX (XX.X%)	XX (XX.X%)
Race			
American Indian or Alaska Native	XX (XX.X%)	XX (XX.X%)	XX (XX.X%)
Asian	XX (XX.X%)	XX (XX.X%)	XX (XX.X%)
Black or African American	XX (XX.X%)	XX (XX.X%)	XX (XX.X%)

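### The SAP narrows the primary analysis set by excluding women with major protocol deviations, a condition the protocol does not contain, the SAP does not define and its change section does not record

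*SAP*

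**What the plan says.** The protocol, section 11 (Analysis Populations), defines an MITT member as a "Safety subject who returns at least 1 tampon that can be assessed for elongation". It sets no other condition. Under Primary Endpoint in the same section it assigns elongation to this set: "Analysis will be done separately for each absorbency for the MITT population".

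SAP section 5 says that the MITT population "includes all safety subjects who have no major protocol deviations and return at least 1 tampon" assessable for elongation. Note [4] to Table 14.1.1 repeats the condition ("The MITT Population includes all subjects in the Safety population who have no major protocol deviations"), as does note [4] to Listing 16.2.3.1, so it is not a slip in one place. SAP section 8.1 reports elongation within test article type "and separately for each absorbency arm, in the MITT population". Section 13.2 lists a single elongation table, Table 14.2.1, "Summary of Elongated Tampons", on MITT.

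On how the condition is applied, SAP section 7.2 says only that deviations are graded minor or major and listed. Section 5 adds: "Assignment of subjects to populations will be determined at a data review meeting prior to database lock". Section 3.6 confirms that the study is open-label. Section 10, "Changes from Planned Analysis", is marked as not applicable.

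**The concern.** The primary result would be reported in a different set of women from the one the protocol names, with no record that the set was changed. The condition is a post-randomisation exclusion without written criteria. The study is open-label, each used-tampon bag carries the product code, and site staff measure elongation at the post-use visits. Neither document says whether deviations are graded without sight of product or elongation, so nothing in writing rules out exclusions related to either.

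The elongation criterion compares two point estimates, and the test product passes if its rate is no higher than the reference rate. With rare events, one or two elongated tampons entering or leaving the analysis can decide a close comparison.

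**Working it through.** **1. The definitions side by side**

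| Item | Protocol | SAP |
|---|---|---|
| Belongs to the Safety population | required | required |
| At least one assessable returned tampon | required | required |
| No major deviation | not mentioned | required |
| Criteria for a major deviation | none | none |
| Used for primary elongation | yes | yes (only table) |
| Change recorded | n/a | none |

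The example of an MITT exclusion in the shell of Listing 16.2.3.1 is that no assessable tampon was returned, which is the protocol's rule alone.

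**2. The plan's sample size**

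Inputs (protocol section 11, Sample Size): elongation 0.7% reference and 0.2% test, two-sided alpha 0.05, power 80%, 7 of 16 tampons used per cycle.

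- Arcsine formula: h = 2(arcsin √0.007 − arcsin √0.002) = 0.07806.
- n = 2 × ((1.960 + 0.842)/0.07806)² = 2,577 tampons per type.
- 2,577/7 rounds up to 369 women; 369 × 7 = 2,583 per type; 2 × 2,583 = 5,166. The plan's figures are reproduced. (SAP section 3.2 prints 2,538 per type, but 2 × 2,538 = 5,076 does not match its own total of 5,166; I use 2,583.)
- The yield of 43.75% is exactly 7/16, so every enrolled woman's used tampons are counted and there is no allowance for excluding women.
- Expected elongated tampons per absorbency: 2,583 × 0.007 = 18.1 reference and 2,583 × 0.002 = 5.2 test. One tampon moves a rate by 100/2,583 = 0.039 percentage points.

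**3. How often one or two events could decide the result**

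Let D = test count − reference count, two independent binomials with n = 2,583 each; pass if D ≤ 0. With denominators held equal, removing one elongated tampon can reverse the result only if D is 0 or 1; removing two, only if D is −1, 0, 1 or 2.

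| True rates (test, reference) | P(D in {0, 1}) | P(D in {−1, 0, 1, 2}) |
|---|---|---|
| 0.7%, 0.7% | 0.0668 + 0.0659 = 13.3% | 26.2% |
| 0.2%, 0.7% (planned) | 0.27% | 0.64% |

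These are upper bounds and cover both directions. At equal rates a one-event reversal in the test product's favour needs D = 1, which is 6.6%.

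**4. Excluding whole women, unrelated to outcome**

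No deviation rate is given, so I assume 18, 37 or 55 of 369 women (about 5%, 10%, 15%). Each takes 7 test and 7 reference tampons with her. With D_K for retained and D_E for removed tampons, the two definitions disagree when exactly one of D_K ≤ 0 and D_K + D_E ≤ 0 is true.

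| Women excluded | Removed per type | Kept per type | Disagree, equal 0.7% | Fail becomes pass / pass becomes fail | P(pass), equal 0.7% | Disagree, planned | P(pass), planned |
|---|---|---|---|---|---|---|---|
| 0 | 0 | 2,583 | – | – | 53.3% | – | 99.8% |
| 18 | 126 | 2,457 | 6.5% | 3.3% / 3.2% | 53.4% | 0.10% | 99.8% |
| 37 | 259 | 2,324 | 9.9% | 5.0% / 4.8% | 53.5% | 0.18% | 99.7% |
| 55 | 385 | 2,198 | 12.3% | 6.3% / 6.0% | 53.6% | 0.26% | 99.7% |

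**5. The supplementary chi-square test**

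Exact power of the Pearson test in SAP section 8.1 is 80.2% at 2,583 per type. It falls to 78.0%, 75.6% and 72.9% when 5%, 10% and 15% of tampons are lost. SAP section 4.1 says that no hypothesis test decides the validation criteria, so this loss does not touch the pass rule.

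**The case against.** The condition is written into an a priori SAP, and populations are fixed before database lock, so it is not a post hoc choice. A SAP may narrow a population. Each woman uses both products and is excluded as a whole, so her test and reference tampons generally leave together, which limits any tilt. Nothing shows that the people grading deviations see elongation data. The planned outputs are also fairly transparent: Table 14.1.1 counts MITT beside Safety, Listing 16.2.2.2 shows major deviations, Listing 16.2.3.1 gives reasons for exclusion, and Listing 16.2.6.1 gives elongation for the whole Safety population. Finally, disagreement of up to 12.3% at equal rates is mostly noise under a rule that is then close to a coin toss; the pass probability moves by 0.3 points at most.

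Much of this stands. It shows that the expected effect of unrelated exclusions is small and that a determined reader could rebuild the protocol-defined result. It also shows that returning to the protocol's definition is not the only acceptable remedy. It does not reconcile the two definitions, supply criteria for a major deviation or correct section 10. A listing from which a result could be rebuilt is not a planned analysis.

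**Conclusion.** The concern holds. Protocol and SAP define the primary population differently, the added condition has no criteria, and the SAP records no change. This should be fixed, but it is not a threat to the trial at its planning assumptions: at 0.7% against 0.2%, excluding up to about 15% of women at random lowers the chance of meeting the elongation criterion from 99.8% to 99.7%. The choice of set matters most if the two products perform alike. The definitions would then give opposite answers in 6.5% to 12.3% of trials, with almost no net shift in either direction. The direction and size of any bias from exclusions related to product or outcome cannot be computed from these documents.

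The figures are per absorbency. They assume independent tampons, 7 used per woman per cycle, equal denominators and the exclusion shares shown. The finding itself assumes that the protocol supplied is the Version 2.0 named in SAP section 1, and that no other document, none being cited, defines a major deviation.

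**What to change.** Preferred: restore the protocol's MITT definition in SAP section 5 and in note [4] of Table 14.1.1 and of Listing 16.2.3.1, and use it for Table 14.2.1. If a set free of major deviations is wanted, give it its own name, use it as a sensitivity analysis, and define a major deviation before the data review.

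If the sponsor keeps the narrower set as primary: record and justify the change in section 10, define a major deviation in advance, preferably with grading done without sight of elongation results, and add an elongation table on the protocol-defined MITT.

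Either route costs SAP wording and at most one extra elongation table. Data collection and sample size do not change.

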6.1. Statistical Definitions and Algorithms

6.1.1. Handling of Dropouts or Missing Data

In general, missing data will not be imputed unless otherwise stated.

6.1.2. Analysis Visit Windows

Analysis visits will be assigned based on the nominal visit recorded in the study database.

6.1.3. Pooling of Sites

Data will be pooled across sites for analysis.

6.1.4. Derived Variables

- Elongated = Any used tampon with a measurement of elongation >10 mm will be considered elongated.

6.1.5. Data Adjustments/Handling/Conventions

All collected data will be presented in listings. Data not subject to analysis according to this plan will not appear in any tables or graphs but will be included only in the data listings.

Adverse events will be coded using the Medical Dictionary for Regulatory Activities (MedDRA; version 25.1) thesaurus. Concomitant medications will be coded using the World Health Organization Drug Dictionary (WHO-DD) Enhanced B3 (September 2022).

The first article insertion date will be the date of the first tampon insertion, that the subject reported, but only for a tampon that has both the date of the tampon's insertion and the date of the tampon's removal documented in the diary. The last article's removal date will be defined in the same manner. The first insertion and last removal dates within each menstrual cycle will be identified using a similar logic but using the data from each menstrual cycle.

In case the subject didn't report the tampon's insertion and removal dates for the 1st menstrual period in the diary but returned at least 1 used tampon from 1st menstrual cycle and has available diary data for the 2nd menstrual cycle, then the first article insertion date and last article removal date for the 1st menstrual cycle will be calculated from the date of post-use visit 2 with the

assumption, that number of days between first tampon's insertion and post-use visits are the same for both menstrual cycles.

If partial adverse event onset dates or partial medication dates occur, the convention for replacing missing dates for the purpose of statistical analysis is as follows: if just day is missing then the day assigned is the first day of the month or the date of first test article insertion (if in the same month), whichever is later; if just month is missing then the month assigned is the month of the first test article insertion, unless that results in a date before the first test article insertion in which case the month after the first test article insertion is used; and if both month and day are missing then the month assigned is the month of the first test article insertion and the day assigned is either the first day of the month or the first test article insertion date, whichever is later.

If partial adverse event onset times occur, the convention is as follows: if the missing time occurs on the day of the first test article insertion and both the hour and minute are missing then the time assigned is the time of the first test article insertion, otherwise if both the hour and minute are missing and the date is not the date of first test article insertion the time assigned is 12:00; if the date is the same as the date of the first test article insertion and only hour is missing the hour assigned is 12 or the hour of first test article insertion, whichever is later, and if the date is the same as the date of first test article insertion and only the minute is missing the minute assigned is 30 or the minute of first test article insertion, whichever is later. Otherwise the hour assigned is 12 if the hour is missing and the date is not the same as the date of first test article insertion and the minute assigned is 30 if the the date is not the same as the date of first test article insertion.

The following precaution will be considered when applying these conventions to adverse event onset dates and times: if the missing date and time reflect the date and time of onset of an adverse event, the modified date and time will be constructed to match the first documented date/time post test article administration while preserving the order in which the adverse event (AE) was reported in the CRF.

7. Study Subjects and Demographics

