9.1. Adverse Events

All AEs and serious adverse events (SAEs) will be coded using the MedDRA v. 25.1.

All AE data will be summarized for 3 periods: before any test article use, during and following test tampon use, during and following reference tampon use. AEs will be assigned to an analysis period based on the below criteria. The criteria for assigning AEs to an analysis period will differ depending on the type of test article (reference or test tampon) first used by the subject.

Test article order	Criteria for assigning AEs to analysis periods
Reference tampon → Test tampon	If the start date of the adverse event was before the date of first insertion of a reference tampon, then the AE will be assigned to the “before any test article use” period. If the start date of the adverse event was on or after the date of first insertion of a reference tampon, but before the date of first insertion of a test tampon, then the adverse event will be assigned to the “during and following reference tampon use” period. If the start date of the adverse event was on or after the date of first insertion of a test tampon, then the adverse event will be assigned to the “during and following test tampon use” period.

Test tampon → Reference tampon	
If the start date of the adverse event was before the date of first insertion of a test tampon, then the AE will be assigned to the “before any test article use” period.
 
If the start date of the adverse event was on or after the date of first insertion of a test tampon, but before the date of first insertion of a reference tampon, then the adverse event will be assigned to the “during and following test tampon use” period.
 
If the start date of the adverse event was on or after the date of first insertion of a reference tampon, then the adverse event will be assigned to the “during and following reference tampon use” period.

--------------------------------	--

An overall summary of AEs will be provided; this will present number and percentage of subjects who reported at least 1 of the following: any AE, AEs by maximum severity, AEs by maximum relationship to study product, AEs by maximum frequency, and SAEs.

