Absorbency Arm: Regular	Variable Statistic	Test Tampon (N=XX)	Reference Tampon (N=XX)
Length of Elongation			
n [1]		XX	XX
Mean (SD)		XX.X (XX.XX)	XX.X (XX.XX)
Median		XX.X	XX.X
Min, Max		XX, XX	XX, XX
Elongated [2]			
n [1]		XX	XX
Percentage		XX.XX%	XX.XX%
95% CI for the Percentage [3]		XX.XXX%, XX.XXX%	XX.XXX%, XX.XXX%
Difference in Percentage		XX.XX%	
95% CI for the Difference in Percentage [4]		XX.XXX%, XX.XXX%	
Chi-Square		XX.X	
P-Value		X.XXX	

Abbreviations: CI = confidence interval; MITT = modified intent-to-treat; SD = standard deviation.

Note: Percentages are n/Number of used tampons returned by subjects in the MITT Population within tampon type*100. Length is measured in millimeters (mm). Tampon integrity assessments were performed at the post-use visits which were conducted within 72 hours following the last tampon use for that menstrual cycle. Subjects used each test article type (reference or test tampon) over the course of one menstrual cycle. N is the number of subjects within each article and within absorbency arm.

[1] n is the number of tampons.

[2] Any used tampon with a measurement of elongation >10 mm was considered elongated.

[3] The 95% CIs for the percentage elongated estimates were computed using the exact method.

[4] The 95% CIs for the difference in percentage elongated estimates were computed using Wald method

Reference Listing: 16.2.6.1

Programming Note: Repeat for Absorbency Arm: Super.

[figure not shown]

Table 14.2.2.1
 Summary of Individual Tampon Entry Diary Responses
 Safety Population

Absorbency Arm: Regular	Test Tampon (N=XX)	Reference Tampon (N=XX)
Variable Category		
Able to remove the tampon	XX	XX
Yes	XX (XX.X%)	XX (XX.X%)
No	XX (XX.X%)	XX (XX.X%)
White area remaining on tampon	XX	XX
No areas on the tampon remained white	XX (XX.X%)	XX (XX.X%)
Less than half of the tampon remained white	XX (XX.X%)	XX (XX.X%)
About half of the tampon remained white	XX (XX.X%)	XX (XX.X%)
More than half of the tampon remained white	XX (XX.X%)	XX (XX.X%)
Whole product remained white	XX (XX.X%)	XX (XX.X%)
Flow when using the tampon	XX	XX
No flow	XX (XX.X%)	XX (XX.X%)
Spotting only	XX (XX.X%)	XX (XX.X%)
Light	XX (XX.X%)	XX (XX.X%)
Medium	XX (XX.X%)	XX (XX.X%)
Heavy	XX (XX.X%)	XX (XX.X%)
Tampons remaining white and where subject reported having any flow when using the tampon*	XX (XX.X%)	XX (XX.X%)

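### The SAP's first insertion date ignores tampons with no recorded removal date, so an adverse event at the start of a cycle can be assigned to the wrong period

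*SAP*

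**What the plan says.** SAP 6.1.5 defines the first insertion date as the earliest one entered in the diary, "but only for a tampon that has both the date of the tampon's insertion and the date of the tampon's removal" on record. The definition carries over to the single cycle: "The first insertion and last removal dates within each menstrual cycle will be identified using a similar logic". Each cycle is devoted to one product (SAP 3.1), so the cycle-level date is in effect the first insertion date of that product.

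The only fallback in 6.1.5 concerns cycle 1. It is for a subject who did not report the cycle 1 dates "but returned at least 1 used tampon from 1st menstrual cycle and has available diary data for the 2nd menstrual cycle". The missing dates are then back-calculated from a post-use visit. Cycle 2 has no counterpart.

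SAP 9.1 uses these dates to attribute events: "All AE data will be summarized for 3 periods", namely before any use, test, and reference. For the reference-first order the opening rule reads "If the start date of the adverse event was before the date of first insertion of a reference tampon", and such an event is placed before any use. Events from that date up to the first test insertion go to reference, and later ones to test. The test-first order mirrors this. Nothing in 9.1 overrides the date comparison when the tampon concerned is known.

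The Safety population in SAP section 5 requires only that one tampon was inserted. Table 14.2.2.1 reports "Able to remove the tampon" as Yes or No for each diary entry, so the plan anticipates that removal can fail.

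**The concern.** Exposure starts at insertion, but the rule makes the start of exposure depend on a later fact, the recorded removal. A tampon with no removal date is treated as if it had not been used when the start of its period is fixed. If it opens the cycle, the period starts too late, and an event in the gap is attributed to whatever came before.

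This deserves attention here because the design change is the placement of the withdrawal string, and being able to remove the product is one of the user needs under validation. Frequency and severity of adverse events feed the tolerability criterion. In the adverse event listing (16.2.7.1) and the serious event listing (Table 14.3.3.1), the study period is the only column that ties an event to a product, so those listings carry the same error. The overall first insertion date also sets study day, the prior or concomitant status of medications (SAP 9.6), and imputed partial dates (SAP 6.1.5).

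**Working it through.** The plan prints no figure for this rule, so the check is to apply the two sections together.

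**Notation.** For each product:
- I = earliest recorded insertion date of any of its tampons
- F = earliest insertion date among its tampons with both dates (SAP 6.1.5)
- s = start date of the event

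With subscripts 1 and 2 for the first and second product used, SAP 9.1 gives: before any use if s < F1; first product if F1 ≤ s < F2; second product if s ≥ F2. An event during use of a product is therefore misplaced exactly when I ≤ s < F. Dates are compared, not times, so the gap is F − I whole days and is zero when a fully dated tampon is inserted on the same day.

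**Constructed diaries, days counted from the start of use:**

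| Case | Diary | Dates | SAP assigns | With I in place of F |
|---|---|---|---|---|
| A | Test first; opening tampon day 1 has no removal date; next fully dated day 3 | I = 1, s = 2, F = 3 | before any use | test |
| B | Reference first; opening test tampon day 29 has no removal date; next fully dated day 31 | I = 29, s = 30, F = 31 | reference | test |
| C | As B, but no further test tampon | I = 29, s = 30, F missing | reference* | test |
| D | Only tampon ever used, day 1, has no removal date | I = 1, s = 2, F missing | no period can be assigned | test |
| E | Reference first; first test tampon day 29 fully dated, second not | F = 29, s = 30 | test | test |
| F | Reference first; test tampon day 29 without removal date, another that day fully dated | F = 29, s = 30 | test | test |
| G | Reference first; removal of the day 29 test tampon entered as day 30 | F = 29, s = 30 | test | test |

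*Case C treats a missing F as a product not yet started. The SAP does not say how a missing date is to be handled, so the result there depends on the programming. The subject in case D is still in the Safety population.

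**Symmetry.** Exchanging the products in A and B gives the mirror errors: a reference event in cycle 1 goes to before any use, and a reference event in cycle 2 goes to test.

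**Cycle 1 fallback.** It can supply a date only if a used cycle 1 tampon was returned and cycle 2 diary data exist. It does not reach B or C (cycle 2), or D (no cycle 2 data). It is worded for a subject who did not report the insertion and removal dates for the cycle, so it does not clearly cover case A, where later tampons are fully dated.

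**Frequency.** The documents give no rate of failed removal or of blank removal dates. As an illustration only: if a single removal failure is equally likely at each of the 7 tampons per cycle assumed in SAP 3.2, then 1/7 = 14.3% of failures fall on the opening tampon. Of these, only cases with no removal date and an event inside the gap are misplaced.

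**The case against.** The strongest reply is that this is a rare edge case with several safeguards.

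- *A failed removal need not leave a blank date.* Listing 16.2.6.2.1 has separate columns for removal date and for ability to remove, so a No can stand beside a date, for instance after help. Protocol section 9 has staff check diary entries for accuracy and completeness and address discrepancies. This stands as a limit on frequency. It does not cure the rule, which has no provision for a date that stays blank.
- *The removal signal survives elsewhere.* Table 14.2.2.1 counts ability to remove over diary entries without requiring a removal date. Every adverse event is listed with dates and relationship, and the Medical Monitor is notified of related non-serious events. Tolerability is judged on review, with no numerical threshold. This also stands: a reader might infer that removal failures disappear from the report, and they do not. What can be wrong is the product to which an associated event is attributed.
- *The rule does not favour either product.* A reader might infer that it shields the test tampon. The documents do not support that: the rule is the same for both products and the order of use is randomized.

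Two further inferences fail. Not every unremoved tampon causes misassignment, because one preceded by a fully dated tampon in its cycle leaves the start date correct (case E). For the same reason, a failure at the last tampon of a cycle does no harm unless no earlier tampon was fully dated.

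**Conclusion.** The point holds in a limited form. SAP 6.1.5 and 9.1, applied as written, send an event to the wrong period when the opening tampon or tampons of a cycle have an insertion date but no removal date, and the event starts on or after that insertion but before the date of the next fully dated one. In cycle 1 the event goes to before any use, and in cycle 2 to the other product. Where no tampon of a product is fully dated, the product has no first insertion date unless the cycle 1 fallback applies.

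This rests on two assumptions. The first is that 9.1 uses the date defined in 6.1.5; 9.1 does not cite that section, but the SAP contains no other definition. The second is that some removal dates remain blank after diary review. The number of affected events cannot be derived and is probably low. It is still a stated rule that gives a wrong answer, not a missing detail, and it should be corrected because the correction is so small.

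**What to change.** In SAP 6.1.5, define the first insertion date, overall and for each cycle and product, as the earliest recorded insertion date of any tampon of that product, whether or not a removal date is recorded. Keep the removal-date condition only for the last removal date. This corrects cases A to D and leaves E to G unchanged.

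Add a sentence for subjects who are known to have used a product but have no insertion date for it, where the cycle 1 fallback does not apply: flag them, and assign their events at the data review meeting that SAP section 5 already schedules before database lock.

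The dispensation date should not be used as a substitute. Under Protocol section 10, subjects outside the gynecological exam subset receive the second product at Visit 2, within 72 hours of the last tampon of the first cycle. Using that date would charge between-cycle events to a product not yet used. In cycle 1 it would empty the pre-use period, because events are collected only from dispensation onward (Protocol section 12).

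The cost is two sentences in the SAP, a small change to the derivation program, and one more item for the data review meeting. No new data are needed.
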